## Protocol Template Form

Item 1 UTHSCSA Tracking Number	HSC20150552H
---------------------------------------	--------------

Item 2 Abstract / Project Summary	
Provide a succinct and accurate description of the proposed research. State the purpose/aims. Describe concisely the research design and methods for achieving the stated goals. This section should be understandable to all members of the IRB, scientific and non-scientific.
 
DO NOT EXCEED THE SPACE PROVIDED.

--	---

**Purpose/Objectives:** The purpose of the proposed study is to examine histologic wound healing following ridge preservation using FDBA compared to PUROS bone allograft.

**Research Design/Plan:** The study is a two-arm, parallel-design, randomized, prospective clinical trial. This entire protocol involves procedures that are standard care. The protocol is similar in design to the protocol our study group has used repeatedly and published in multiple papers.

**Methods:** Subjects will have a non-molar tooth extracted and the socket grafted with one of two different bone graft materials (FDBA or PUROS). At the time of implant placement 12 weeks after tooth extraction a small core biopsy specimen will be removed from the implant site. Clinical measurements of the ridge dimensions will be taken at the time of tooth extraction and again at the time of implant placement. The core biopsy will then be evaluated for the primary outcomes: % vital bone formation, % residual graft material, and % “CT/other” (fibrous tissue and marrow space). We will also be evaluating the following secondary outcomes using a custom measuring stent for each subject: change in ridge width; change in buccal ridge height, and change in lingual ridge height.

**Clinical Relevance:** Having a high percentage of new vital bone after tooth extraction and ridge preservation may be beneficial in maintaining ridge dimensions for implant placement. This study will examine differences in vital bone formation with FDBA VS. PUROS

Item 3 Background	

Describe past experimental and/or clinical findings leading to the formulation of your study.
 
For research involving unapproved drugs, describe animal and human studies.
 
For research that involves approved drugs or devices, describe the FDA approved uses of this drug/device in relation to your protocol.
	
Insert background: Bone grafting following tooth extraction is commonly performed to preserve bony ridge dimensions adequate to support subsequent implant placement. Alveolar ridge resorption often occurs following tooth extraction, and the decrease in bone volume has the potential to make dental implant therapy impossible without surgery to reconstruct the ridge. The aim of ridge preservation grafting is to prevent or minimize this resorptive process, thereby preserving an adequate volume of bone for implant placement. Ridge preservation generally involves placement of a particulate bone graft material in the tooth socket, followed by use of a membrane or similar substance over the socket entrance to contain the bone graft. Various grafting materials have been recommended for these ridge preservation procedures, including cortical and cancellous freeze-dried bone allograft (FDBA), demineralized freeze-dried bone allograft (DFDBA), allografts processed without freeze-drying, various xenografts, alloplasts and autografts.
 
Our research group has published several studies evaluating a variety of materials for ridge preservation. Beck & Mealey examined healing using a non-freeze-dried bone allograft prepared using the proprietary Tutoplast process (PUROS) and found similar new vital bone formation following a healing period of 3 months versus 6 months after ridge preservation. In both groups, newly formed vital bone constituted approximately 45% of the total volume of the histologic specimens. In Wood & Mealey the use of cortical DFDBA provided a higher percentage of new vital bone formation (38.4%) than did cortical mineralized FDBA (24.6%). A major strength of this study was that the comparison graft materials for both study groups

came from the same tissue donor, eliminating any issues that might arise from using different donor sources. Similarly, two additional studies done by our research group used a single source of donor bone for both study treatment groups.

Our research group examined the effect on new bone formation of ridge preservation procedures performed using either cortical or cancellous FDBA. There was no significant difference in new vital bone formation between the cortical (median 16.1%) and cancellous (median 13.0%) FDBA groups. A significantly greater percentage of residual graft material was detected in the cortical FDBA group as compared to the cancellous FDBA group, and a significantly greater percentage of nonmineralized CT/other material was found in the cancellous FDBA group as compared to the cortical FDBA group. Finally, we have recently completed a study comparing 100% cortical FDBA to a combination of 70% cortical/30% cancellous FDBA. The combination allograft resulted in increased vital bone percentage, (36.2%) compared to the 100% FDBA group (24.7%).

In reviewing the vital bone formation we have seen across multiple studies when FDBA was used in one or more study arms, it is noteworthy that the amount of new bone formation seen with the mineralized non-freeze-dried PUROS allograft used in Beck & Mealey (approximately 45% new bone) was higher than that seen when mineralized freeze-dried bone allograft was used (approximately 13-25%). However, there are no published direct comparison data evaluating FDBA versus bone allograft processed via the Tutoplast process (PUROS) when used for ridge preservation after tooth extraction.


Item 4 Purpose and rationale Insert purpose, objectives and research questions/hypotheses here. If you cut and paste from another document, make sure the excerpted material answers the question
	
Insert purpose: The study is designed to examine histologic wound healing following ridge preservation using with mineralized freeze-dried bone allograft (FDBA) or mineralized bone allograft prepared via the Tutoplast process which does not involved freeze-drying. This entire protocol involves procedures that are standard care. The study is a 2-arm, parallel-design, randomized, prospective clinical trial. The test group subjects will have extraction sockets grafted with a PUROSE. This test group will be compared to an active control group using FDBA as the graft material. The null hypothesis is that there will be no significant difference in formation of new vital bone between treatment groups (primary outcome). In keeping with the protocol our study group has used several times before, the plan will be to extract non-molar teeth and graft with the test/control materials. Each subject will provide a single non-molar tooth site for study treatment. The graft material will be covered with a resorbable bovine pericardium membrane (called CopiOs). Following 12 weeks of healing, we will place the dental implant. To place a dental implant, an osteotomy (hole in the bone) is prepared into which the implant is placed. This osteotomy can be prepared with either a solid drill, in which case the bone that is removed is suctioned into the suction system, or with a hollow trephine drill into which a core of bone can be collected. The only "research procedure" being done in the current study is the collection of this bone core biopsy for histologic evaluation. The core biopsy will then be evaluated for the primary outcomes: % vital bone formation, % residual graft material, and % "CT/other" (fibrous tissue and marrow space). We will also be evaluating the following secondary outcomes using a custom measuring stent for each subject: change in ridge width; change in buccal ridge height, and change in lingual ridge height.

Item 5 Study Population(s) Being Recruited
 
In your recruitment plan, how many different populations of prospective subjects do you plan to target? Provide number: 1
	
Identify the criteria for inclusion:
	
Identify the criteria for exclusion:


e.g., a population can be individuals with type 2 diabetes controlled with diet and/or a population of healthy controls. Or a population can be individuals attending an education program, etc.
 
List each different population on a separate row and provide a short descriptive label: (e.g., normal-healthy, diabetics, parents, children, etc.)
 
To add rows use copy & paste
		

Patients seen in Periodontics
	
 
• A single rooted tooth that has
 
	
 
• who will not cooperate with the
 

	
been identified by dental faculty as requiring extraction
 
 
• Desire a dental implant to replace the missing tooth
 
• Have adequate restorative space for a dental implant-retained restoration
 
• Have at least 10mm of alveolar bone height, without impinging on the maxillary sinus or inferior alveolar canal.
 
• Have a dehiscence of the buccal or lingual bony plate of the tooth socket extending no more than 50% of the total depth of the socket.
 
• Female patients who have undergone a hysterectomy, tubal ligation, or menopause, and non-pregnant women of child-bearing potential.
 
• Are nonsmokers or former smokers. Current smokers may be included if they smoke <math>\leq 10</math> cigarettes per day
 
	
follow-up schedule.
 
 
• Patients will be mentally incompetent, prisoners, or pregnant.
 
• Pregnant women or women intending to become pregnant during the study period. Prior to dental surgery, females of child-bearing age are asked verbally if there is any possibility that they are pregnant. If not, we proceed with surgery and no pregnancy test is done. If the woman states that there is a possibility that she is pregnant, we do a urine pregnancy test to rule pregnancy in or out. So use of the urine pregnancy test is only done if she says she may be pregnant. [If needed: An over-the-counter urine pregnancy test will be provided to female subjects in the graduate periodontics clinic of UTHSCSA. Subjects will be allowed access to a private restroom and the results of the tests will be read by one of the named investigators. Only those with a negative pre-operative pregnancy test will continue in the study.] Grafted patients who become pregnant during the study will be withdrawn, but will be followed until completion of pregnancy.
 
• Smokers who smoke <math>>10</math> cigarettes per day
 
• Clinical and/or radiographic determinations which will preclude inclusion in this study are: Active infection other than periodontitis; Inadequate bone dimensions or restorative space for a dental implant; Presence of a disease entity, condition or therapeutic regimen which decreases probability of soft tissue and bony healing, e.g., poorly controlled diabetes, chemotherapeutic and immunosuppressive agents, autoimmune diseases, history of bisphosphonate use or long-term steroid therapy; Positive medical history of endocarditis following oral or dental surgery. Sensitivity or allergy to Bacitracin, Gentamicin, Polymyxin B Sulfate, alcohol and/or surfactants (per package insert)
 

Insert response here	Insert response here	Insert response here

**Item 6**

**Research Plan / Description of the Research Methods a.** *Provide a comprehensive narrative describing the research methods. Provide the plan for data analysis (include as applicable the sample size calculation).*

Step-by-Step Methods: The purpose of the proposed study is to examine histologic wound healing following ridge preservation using FDBA compared to PUROS bone allograft. The study is a two-arm, parallel-design, randomized, prospective clinical trial. This entire protocol involves procedures that are standard care. The protocol is similar in design to the protocol our study group has used repeatedly and published in multiple papers.

There will be two subject groups in this study. All subjects will require extraction of at least one non-molar tooth, followed by replacement of the missing tooth with a dental implant. If a given subject requires more than one tooth extraction, only one tooth site will be included in the study (the site with the best bony walls present after extraction; if two or more sites have equally good bony walls, the study site will be selected randomly by coin toss if there are two teeth to be extracted, or by drawing a number from a hat if more than 2 teeth require extraction). Based on power analysis and drop-out experience from previous studies, a total of 22 subjects will be recruited per group, with a maximum enrollment of 44 subjects for the 2 groups combined.

**Test group** subjects will have extraction sockets grafted with cancellous PUROS mineralized bone allograft (prepared using the Tutoplast process). This test group will be compared to an active **control group** in which extraction sockets are grafted using cancellous mineralized freeze-dried bone allograft (FDBA). Allocation of subjects into test or control group will be based on numbers drawn from a stack of sealed envelopes. At the beginning of the study there will be 22 envelopes containing a piece of paper inscribed with "Group 1" and 22 envelopes with "Group 2" (Group 1= cancellous PUROS; Group 2 = cancellous mineralized FDBA). The subjects will not be randomized until after the tooth to be extracted has been removed (see below).

At the time of subject enrollment, the following standard procedures will be performed: impressions will be made for fabrication of diagnostic casts. The tooth or teeth to be extracted will be noted on the casts. Radiographs will be taken of the tooth or teeth to be extracted. A clear resin measuring stent will be fabricated in the laboratory to allow standardization of the location of clinical measurements of ridge width and height. A small flap will be reflected to an extent about 3mm beyond the bony walls of the socket. The measuring stent will be placed and measurements of ridge width and ridge height will be taken and recorded to the nearest 0.5mm. Ridge width will be measured using a ridge caliper at a point approximately 4mm apical to the facial and lingual bony crest through small holes created in the stent at those locations. Ridge height will be measured through two holes in the occlusal aspect of the stent – one hole directly above the facial bony crest and another hole directly above the lingual bony crest. This stent will be retained for use during the subsequent implant placement surgery.

The tooth will be extracted, and the number of bony walls in each socket will be recorded along with the presence of any bony dehiscences or fenestrations. Buccal and lingual flap elevation will be minimized and will extend only approximately 3mm beyond the bony crest on the facial and lingual surfaces. The buccal plate thickness will be measured using an Iwanson gauge positioned perpendicular to the inner wall of the extraction socket. One beak of the gauge will be placed within the extraction socket 1.0mm below the alveolar bone crest. The other beak will be placed on the external bone surface. This buccal plate thickness measurement will be recorded to the nearest tenth of a millimeter. **The subject will then be randomized by drawing a sealed envelope from the stack.** The socket will be thoroughly debrided, and either cancellous PUROS or cancellous FDBA will be placed in the socket to restore the ridge to appropriate contour. A CopiOs bovine pericardium resorbable collagen membrane will then be placed over the socket orifice extending about 3mm beyond the bony socket walls. Sutures will be placed over the membrane to secure it in place. Primary closure will not be attempted. Dehiscences of the bony walls of the socket may be found during the extraction procedure, as they are relatively common. **If the dehiscence is deeper than 50% of the total socket depth, the subject will be withdrawn from the study.** If the dehiscence is less than 50% of the depth of the socket, a larger flap will be reflected so that the CopiOs membrane can extend 3mm beyond the bony walls of the dehiscence. The patient

will be seen 7-10 days after extraction/ridge preservation to assess healing, and again 1 month after the procedure.

At the time of implant placement approximately 12 weeks after extraction and ridge preservation, the individual subject's measuring stent and caliper will be used to determine the ridge width and ridge height at the same locations as done in the tooth extraction/grafting surgery visit. The first osteotomy will be prepared using a hollow trephine with internal diameter of 2.0mm instead of a solid drill. The trephine drill will be used to a depth of approximately 8mm, ensuring that the bone within the trephine comes from the former socket area and not from surrounding native bone. The bone removed from the osteotomy site remaining in the trephine will be prepared for histologic examination and analyzed for new bone growth. The histologic cores will be processed for demineralized sections and will be stained. The following histologic parameters will be measured: percent new bone formation, percent residual graft material, and percent connective tissue/other. A surgical guide stent will be fabricated on the diagnostic casts and will be used to ensure proper positioning of the trephine at the site of the grafted ridge preservation procedure. Following initial preparation of the implant site with the trephine, the osteotomy will be completed and an implant of the appropriate length and diameter will be placed. The size of the implant will be such that it will engage not only newly formed bone in the socket itself, but at least 2-3mm of bone apical to the former socket site. A healing abutment will then be placed. The study itself will end at the time of the bone core removal. All subjects will be examined at 7-10 days following implant placement and at several visits between implant placement and final determination of implant stability for restoration, usually about 3-5 months after implant placement. The patient will then be referred to his/her restorative dentist for final restoration.

At the 12 week post-extraction/ridge preservation visit, in cases where the bone width or bone density is insufficient for implant placement at the time of osteotomy preparation with the trephine drill and subsequent implant drills, the implant will not be placed. Instead, guided bone regeneration will be performed in the usual manner and the site will be allowed to heal for 4-5 months before implant placement. As for all subjects, the study itself will end at the time of bone core removal.

Data Analysis Plan: The primary hypothesis to be tested is whether the mean percentage of new bone observed histologically for patients receiving a mineralized cancellous PUROS graft for ridge preservation in an extraction site prior to implant placement is different than those receiving a mineralized cancellous FDDBA graft at a time point approximately 12 weeks after grafting. The distribution of new bone percentages is expected to be positively skewed, conforming to a double exponential distribution. The hypothesis will be tested using a Mann-Whitney U test. A total of 44 patients will receive treatment in a non-molar tooth site, with a minimum of 70% of patients expected to be fully compliant under the study protocol, so that the sample size available for histologic examination will be at least 14 patients per treatment group. This proposed sample size is sufficient to detect a mean difference of one standard deviation or more by Mann-Whitney U test at the 0.05 level with power of 88.5%. For example, if the population standard deviation of new bone percentage within patients is 10% or less, then the proposed sample is sufficient to detect a clinically significant mean difference of 10% or more new bone for patients receiving PUROS compared to FDDBA.

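### The envelope is written to be drawn before the socket is debrided, and nothing keeps the allocation from the operator during that step

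*Combined protocol and SAP*

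**What the plan says.** The Step-by-Step Methods in Item 6 state that randomisation waits until the tooth is out. The extraction-visit paragraph then gives the steps in this order:

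1. The tooth is extracted and the socket is described: "the number of bony walls in each socket will be recorded along with the presence of any bony dehiscences or fenestrations".
2. Buccal plate thickness is measured with a gauge: "One beak of the gauge will be placed within the extraction socket 1.0mm below the alveolar bone crest".
3. Allocation follows: "The subject will then be randomized by drawing a sealed envelope from the stack".
4. The next sentence covers debridement and grafting together: "The socket will be thoroughly debrided, and either cancellous PUROS or cancellous FDBA will be placed in the socket".
5. The membrane and sutures are placed.

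Each envelope holds a group number, and the protocol prints the key: "Group 1= cancellous PUROS; Group 2 = cancellous mineralized FDBA". Debridement is mentioned nowhere else. The document does not say who draws or opens the envelope, or when the operator learns the group.

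**The concern.** The operator has to know the arm in order to place the graft, but does not need to know it to clean the socket. Debridement is common to both arms, and how far it is taken is left to the operator's judgement. If the arm is known at that moment, the socket could be prepared differently in the two arms.

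The primary outcome, percent vital bone, is read from a core taken from that same socket. The document provides for no record of the extent of debridement, so a difference in preparation could not later be separated from an effect of the graft.

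The setting is not neutral. The background in Item 3 contrasts about 45% new bone with PUROS in one earlier study with about 13-25% for mineralised FDBA in others. An operator who has read the protocol may therefore expect PUROS to form more bone.

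**Working it through.** The plan gives no figure on this point, so the check is a reading of the text in sequence.

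**Order of the draw and debridement.** The randomisation sentence carries the word *then*, which places it after the plate-thickness measurement. The debridement sentence comes directly afterwards. Because debridement appears only once, no other text puts it before the draw.

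**Protection of the operator's knowledge.** I looked for three things in Items 2, 4 and 6:
- masking of the operator;
- a second person who holds the envelope until the socket is ready;
- a standard for debridement beyond the instruction that it be thorough.

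None of these is present. The group numbers give no concealment once an envelope is opened, because the protocol prints their meaning.

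**What already precedes the draw.** Extraction, the wall count, the record of dehiscences and fenestrations, and plate thickness are all written before the envelope. The plan thus already keeps most socket work ahead of allocation. Debridement is the one remaining step before grafting that does not need the allocation, and it is written after the draw.

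**Extent.** There are 22 envelopes per group, and 22 + 22 = 44, so up to 44 subjects are affected. The Data Analysis Plan expects at least 14 per group to be available for histology. No input in the document allows a shift in percent vital bone to be calculated, so none is given here.

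**Effect of the change on the design figures.** The stated power of 88.5% rests on 14 per group, a difference of one standard deviation, the Mann-Whitney test and the 0.05 level. The time at which an envelope is opened enters none of these, so moving the draw alters none of them.

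**The case against.** **The paragraph is not strictly chronological.** It describes limited flap elevation after extraction, although the preceding paragraph has already reflected a flap. It also gives the rule "If the dehiscence is deeper than 50% of the total socket depth, the subject will be withdrawn from the study" after the membrane and sutures, although it concerns defects found during extraction. The debridement sentence has no time word of its own. This stands to the extent that actual practice may differ from the written order. It does not remove the point, because the only order the text gives puts debridement after the draw.

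**The bias is speculative and the remedy partial.** Both arms have the same instruction, both materials are described as in common clinical use, and the hypothesis is non-directional. After the change the operator would still know the arm while filling the socket and placing the membrane, and nothing masks the person who takes the core. All of this is correct, and it keeps the point small. It does not justify leaving open a step that can be closed at almost no cost.

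**Stronger readings that the document does not support:**
- *The surgeon debrides knowing the graft.* This is an inference. The text does not say who opens the envelope or when the operator is told. What can be said is that nothing prevents it.
- *The socket baselines are compromised because they are taken before cleaning.* These measures are written before the draw, so allocation cannot influence them, and any inaccuracy would affect both arms alike. The Data Analysis Plan assigns them no baseline comparison or adjustment. Ridge width and height, the baselines for the secondary outcomes, are taken through the stent and described before extraction. The document does not support a criticism of the order of measuring and debriding, and none is made here.

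**Conclusion.** The point holds in a limited form. As written, allocation precedes an operator-dependent step that is identical in both arms and does not need the allocation, and nothing in the document keeps the allocation from the operator during it. That is a small, avoidable route for performance bias on percent vital bone, present for every randomised subject.

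Neither the size nor the existence of an actual bias can be shown from the document. The conclusion rests on two assumptions: that the written order reflects practice, and that the operator could learn the group when the envelope is opened. If practice already finishes socket preparation first, the remaining fault is that the text does not say so.

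**What to change.** In the extraction-visit paragraph of Item 6, move the randomisation sentence. The envelope should be drawn and opened only after debridement and all socket assessment (bony walls, dehiscences, fenestrations, plate thickness) are complete, and immediately before the assigned graft is placed. The order of debridement and measurement relative to each other need not change. It would help to add who opens the envelope.

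The cost is an edit to one sentence and an envelope opened a few minutes later. No procedure, visit or member of staff is added, and sample size, significance level and power are unaffected. The change does not mask graft placement or core removal, which remain open to the operator.

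### Could a subject be withdrawn for a deep dehiscence after the envelope is drawn, and does the plan need changing for it?

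*Combined protocol and SAP*

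**What the plan says.** Item 5 admits a buccal or lingual dehiscence "extending no more than 50% of the total depth of the socket". It gives no time of assessment.

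Item 6, on allocation, states: "The subjects will not be randomized until after the tooth to be extracted has been removed". On the stock of envelopes it says "At the beginning of the study there will be 22 envelopes" for Group 1; Group 2 has the same number, and enrollment is capped at 44.

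Item 6, on surgery, describes what is noted once the tooth is out: "the number of bony walls in each socket will be recorded along with the presence of any bony dehiscences or fenestrations". Buccal plate thickness is then measured, and after it: "The subject will then be randomized by drawing a sealed envelope from the stack". Debridement, graft, membrane and sutures are described next. Only then does the text return to dehiscences: "Dehiscences of the bony walls of the socket may be found during the extraction procedure, as they are relatively common". The withdrawal rule follows, "If the dehiscence is deeper than 50% of the total socket depth, the subject will be withdrawn from the study", and then the handling of smaller defects: "If the dehiscence is less than 50% of the depth of the socket, a larger flap will be reflected".

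The Data Analysis Plan in Item 6 has 44 patients treated, at least 70% compliant, at least 14 per group with histology, and 88.5% power for a difference of one standard deviation (SD) by Mann-Whitney test.

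**The concern.** Read in sentence order, the withdrawal rule comes after the draw. What is listed before the draw is the presence of a dehiscence, not its depth, so the 50% threshold rests on a value that nobody is told to keep. An operator who has opened the envelope could then judge a borderline socket knowing the graft material. If that judgement leaned one way by arm, the analysed groups would no longer be the randomized groups. The Mann-Whitney test cannot repair that, and a later reader could not check the depths.

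There is also an accounting question. The envelopes number exactly 22 + 22, the cap is 44, and 44 are to be treated, yet nothing says whether a withdrawn subject's envelope is reused or the subject replaced. Losses of this kind could take the evaluable number below 14 per arm.

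**Working it through.** **1. The plan's own figure.** The inputs, from the Data Analysis Plan, are 14 per group, a difference of 1 SD, alpha 0.05 and a double exponential outcome. The test is taken as two-sided, which the hypothesis wording implies but does not state. The large-sample efficiency of Mann-Whitney relative to the t test for this distribution is 1.5, so the effective size is 14 × 1.5 = 21 per group. Two-sided noncentral t power is then 0.8853, which matches the stated 88.5%.

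**2. Order of events.**
- The 50% limit is an inclusion criterion (Item 5), and eligibility precedes allocation.
- Randomization waits until the tooth is out. The steps described between extraction and the draw are socket assessment: walls, dehiscences, fenestrations and plate thickness.
- Dehiscences are said to be discovered while the tooth is being extracted, which is before the draw.
- Sentence position proves nothing. The larger-flap instruction also follows the suturing text, although it must be carried out before the membrane goes in.
- Withdrawal need not mean after randomization. Item 6 places enrollment, with casts and stent, before surgery, so an enrolled subject who fails the socket check before the draw is correctly called withdrawn.

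No sentence says that the limit is applied after the envelope is opened.

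**3. Size of the bias if it were.** The documents give no withdrawal count and no correlation, so both are assumed. There is no true difference, with 22 per arm. Subjects lowest on a baseline factor correlated 0.3 to 0.5 with 12-week bone are removed after the draw. Outcomes are normal or double exponential. The test is the exact two-sided Mann-Whitney at 0.05, with 40,000 trials per setting (Monte Carlo standard error about 0.001).

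| Removal after the draw | Bias (SD) | Type I error |
|---|---|---|
| None | 0 | 4.9–5.1% |
| Equal in both arms (2+2 or 4+4) | within 0.004 of 0 | 5.0–5.7% |
| 3 in one arm, 1 in the other | 0.04–0.08 | 5.0–6.0% |
| 2 to 4 in one arm only | 0.05–0.15 | 4.9–7.7% |
| 2 to 4 in one arm only, then random loss to 14 per arm | 0.05–0.16 | 5.1–7.2% |

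The one-arm case removes 2/22 = 9% to 4/22 = 18% of that arm and none of the other, which is close to a worst case. At the plan's example SD of 10 points, a bias of 0.05–0.16 SD is 0.5–1.6 points, against the 10-point difference the plan aims to detect.

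**4. Places and envelopes.** Evaluable per arm = 0.70 × (22 − k), where k is the number lost per arm outside the 30% allowance:
- k = 0: 15.4
- k = 2: 14.0
- k = 3: 13.3
- k = 4: 12.6

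The minimum of 14 fails only at k = 3 or more. By the method in step 1, power is 86.0% at 13 per group and 83.0% at 12. Exact power simulated on double exponential data is lower (80.6% at 14, 75.3% at 13). That gap comes from the large-sample efficiency factor and is a separate question.

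**The case for a change.** The strongest opposing case is that presence is not depth. The protocol records plate thickness to a tenth of a millimetre but keeps no value for the one socket measurement that removes a subject, so adherence to the intended order cannot be shown afterwards. The plan itself calls dehiscences common, although it gives no rate for those beyond 50%. The accounting gap also survives a check before the draw: a subject who fails after extraction is already enrolled, and if that subject counts toward the cap of 44, a single such withdrawal makes 44 treated unreachable.

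The omissions stand as facts. Their consequences do not reach the result. Number of walls and presence of dehiscences are recorded before the draw, so socket defects can be compared by arm, though not by depth. The requirement behind the power claim is 14 evaluable per group, not 44 treated. If withdrawals before the draw do count toward the cap and fall outside the 30% allowance, four in total split evenly still leave 0.70 × 40 / 2 = 14.0 per arm. Item 6 also bases the 22 per group on drop-out seen in previous studies, so the allowance may already include such losses, and 15.4 would then stand.

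One smaller slip is real. Item 5 admits a dehiscence of exactly 50% and Item 6 withdraws only deeper ones, but the larger-flap sentence covers only those below 50%. The investigators must reconcile these sentences. Neither allocation nor analysis depends on it.

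**Conclusion.** The concern identifies detail that is not written down, but not a flaw in the design. On the natural reading the limit is confirmed before the envelope is drawn, bias from this source is nil, and dehiscence uses up no envelope. The simulated type I error of up to 7.7% rests on removal after the draw, from one arm only, by discretion, for a factor linked to outcome. The documents support none of these steps, and equal removal leaves the estimate unbiased. The sample size margin absorbs up to two lost places per arm, and more if the 30% allowance already covers them.

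This is a gap that a surgical team and analyst would fill sensibly by checking eligibility before opening the envelope and accounting for any withdrawal by arm. The conclusion rests on that reading of the order of events, which the text implies without stating. Evidence of withdrawals made after the draw would change it.
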